1. SUMMARY

Rationale: A fecal immunochemical test (FIT)-based colorectal cancer (CRC) screening program was implemented in the Netherlands in 2014. Nearly 15,000 patients are yearly diagnosed with a *large complex (non-pedunculated) colorectal polyp* (LNPCP) for which endoscopic resection is the first-line therapy. LNPCPs carry a high malignant potential. Endoscopic resection of LNPCPs is technically challenging, with a risk of local recurrence, repeat colonoscopy and additional surgery, resulting in a negative impact on clinical outcome, patient's quality of life, and increased colonoscopy burden for repeat procedures.

Objective: Development of a standard training program for advanced endoscopic resection techniques is urgently needed to improve outcomes at both a patient and program level. Improvement of *education* and *colonoscopy training* is the first key-step.

- (I) **A.** To develop a systematic training program for treatment of LNPCPs
- B.** To investigate if additional training improves clinical outcomes
- (II) To assess the impact of performing endoscopic resection for LNPCPs on the patients quality of life (QoL).
- (III) To perform an economic analysis comparing post-training endoscopic resection vs. common endoscopy practice vs laparoscopic surgery.

We hypothesize that a series of measures, i.e. *a priori* endoscopic and histological diagnosis followed by a therapeutic plan and high-quality endoscopic resection performance will improve outcome.

Study design: A multicenter randomized controlled trial (RCT) will be conducted to compare the performance of additionally trained endoscopists (n=15 centers, n=30 endoscopists) vs. regularly trained endoscopists (control group; n=15 centers, n=30 endoscopists).

The period of inclusion and follow-up will be from 2019-2021, where the duration of the follow-up of an individual patient will be 6 months, confirm the current guidelines.

Study population: Patients (18 years and older) who have an indication for colonoscopy, in particular patients from the nationwide screening program.

Inclusion criteria for participating endoscopists will be:

1. Experienced endoscopists (i.e. total number of colonoscopies performed will be at least 250 procedures under supervision plus 500 colonoscopies independently) including documentation of the key-performance indicators (cecal intubation rate, adenoma detection rate and polypectomy rate)

Intervention (if applicable): The intervention group will comprise 30 endoscopists (from 15 centers) who receive the additional training package. The control group will comprise 30 endoscopists (from 15 centers) who receive regular training.

Participating centers will be randomized to the *intervention group vs. control group*. To mitigate the effect of contamination, i.e. exchange of knowledge, practical skills between participants, we prefer to randomize centers instead of endoscopists. In each center two endoscopists will participate in the study.

Main study parameters/endpoints:

- Primary endpoints: local recurrence rate (6 months after resection).
- Secondary endpoints: radical (R0) resection rate, complication rate, number of repeat colonoscopies, referral rate to surgery and patient satisfaction regarding clinical outcomes of endoscopic resection (at two or three time points (before endoscopic resection (is not applicable in all cases)/1 week after endoscopic resection/6 months after endoscopic resection) and cost-effectiveness (post-training situation vs current situation vs laparoscopic surgery).

Nature and extent of the burden and risks associated with participation, benefit and group relatedness:

This project aims to provide the fundamentals for best practice in the treatment of large complex (non-pedunculated) colorectal polyps (LNPCPs). Increased quality and effectiveness of endoscopic resection of LNPCPs will reduce CRC incidence. The project proposes strategies to reduce the patient burden (additional colonoscopy and surgical procedures) and risk of complications, which in turn will improve patient's quality of life and the effectiveness and efficiency of the national population screening program.

2. INTRODUCTION AND RATIONALE

Professionalism in the colonoscopy practice clearly changed the clinical course of colorectal cancer (CRC). Both CRC incidence and mortality continue to decline {Nishihara, 2013;Zauber, 2012}. With the introduction of the nationwide FIT-based CRC screening program, nearly 15,000 patients are yearly diagnosed with large (≥ 2 cm) complex (non-pedunculated) colorectal polyps (abbreviated as LNPCPs), for which endoscopic resection is the first-line therapy. The post-colonoscopy CRC rate did not drop over the past decade {Pullens, 2015;le Clercq, 2014}. Besides missed cancer/ precursors, incomplete polyp resection explains at least 20% of all PCCRCs {Robertson, 2014}, a situation which must be clearly improved.

Recent guidelines of gastrointestinal professional societies provide a conceptual basis to perform endoscopic treatment for LNPCPs {Pimentel-Nunes, 2015;Rutter, 2015}. In clinical practice, endoscopic resection outcomes vary and are far from perfect. As the nationwide screening program progresses, it is important to optimize performance and outcomes of endotherapy.

Two recent meta-analysis examined the local recurrence rate after endoscopic resection of large colorectal polyps {Belderbos, 2014;Ortiz, 2014}. Belderbos et al. showed local recurrence rates in 15% (95% CI: 12-19%) of cases after endoscopic resection of nonpolypoid neoplasms. Ortiz et al. reported a local recurrence rate of 13.1% after resection of both polypoid and nonpolypoid neoplasms. Several factors are associated with risk of local recurrence with the most common ones being proximal location, lesion size and shape {Moss, 2011}. Importantly, piecemeal (instead of en-bloc) resection is often associated with local recurrence (OR 4.39, 95% CI: 2.05-9.41; 20%, CI: 16-25%) {Ortiz, 2014;Belderbos, 2014}. Studies from Japan showed a 4-times more frequent recurrence rate for piecemeal resection of LSTs (granular type) than en-bloc resection {Oka, 2015}. Another meta-analysis on the efficiency and safety of endotherapy for large (≥ 20 mm) colorectal polyps showed that 8% (95% CI: 7-10%) of such patients required additional surgery because of a non-curative endoscopic resection. An important finding was that >90% of the recurrences could be successfully treated by additional endoscopic therapy {Hassan, 2015}.

To ensure en-bloc resection of lesions with high suspicion of malignancy, the endoscopic submucosal dissection (ESD) technique should be adopted. Practical performance of ESD is however difficult and requires a long and steep learning curve, additional equipment and longer procedural time {Saito, 2001}. Risk of perforation is also higher for ESD vs EMR: 5.4% (1.3%-20.4%) vs. 0.7% (0%-6%) {Tanaka, 2013}. A strategic multistep plan is therefore

required to implement ESD in the Western endoscopy practice {Sanduleanu, 2016}. Pre-treatment diagnosis of the depth of submucosal (SM) invasion which takes into consideration lesion appearance, epithelial surface pit-pattern and vascular pit-pattern is a key-step towards successful endotherapy {Yamada, 2016}. Additional technical and non-technical (logistic, strategic) skills are required. As this takes considerable time, referral to specialized centers where complex endotherapy can be performed in a timely manner is recommended in the meantime {Rutter, 2015}. For example, in the case of a LNPCP ≥ 20 mm in size, with a non-invasive pit-pattern, the lesion is likely an adenoma, or intramucosal cancer (Tis) or superficial submucosal invasive carcinoma (T1a cancer, i.e. SM invasion depth $< 1000\mu\text{m}$, sm1) with a very low risk of lymph node metastasis and ESD is the preferred therapy {Kitajima, 2004; Nakajima, 2013}. When deep submucosal invasive cancer (T1B cancer, i.e. SM invasion depth $> 1000\mu\text{m}$, sm 2-3) is suspected, given the high risk of lymph node metastasis, surgery is recommended {Yamada, 2016}.

Differentiation of an invasive from a non-invasive epithelial surface pit-patterns is challenging and ideally requires magnifying chromoendoscopy {Hayashi, 2013}. A large prospective study at the National Cancer Center in Tokyo (Japan) showed a sensitivity, specificity and diagnostic accuracy of differentiating mucosal cancer or superficial (sm1) invasion from deeper (sm2-3) invasion using magnifying chromoendoscopy of 85.6%, 99.4% and 98.8%, respectively {Matsuda, 2008}. A recent study of the same group showed the importance of a thorough macroscopic examination. Because both *granular type* LSTs with a large nodule or depression and *non-granular type* LSTs are associated with a substantial risk of submucosal (SM) and multifocal invasion, *en-bloc* endoscopic resection is the preferred therapy in such cases {Yamada, 2016}.

2.1 OBJECTIVES

This project aims to integrate current knowledge and technical expertise on treatment of LNPCPs from leading centers worldwide in the Dutch colonoscopy practice. Development of a standard training program to be supported by education and structured training is a prerequisite for best practice in the management of LNPCPs.

2.1.1 Primary Objective:

To investigate if systematic stepwise training improves the outcome of endoscopic treatment for LNPCPs, i.e. local recurrence (6 months after resection), radical (R0) resection rate, complication rate and referral rate to surgery.

2.1.2 Secondary Objective(s):

The patient's quality of life (QoL) will be assessed. Because a validated questionnaire is not yet available, we will adapt the Medical Outcomes Study Short Form 36 {McHorney, 1993;Ware, 1992} and a colorectal-specific European Organisation for Research and Treatment of Cancer (EORTC) QoL questionnaire {Theodoropoulos, 2013}. Questionnaires will be applied at two or three time points, depending on logistics in the particular hospital (see 5.3; study procedures).

[figure not shown]
To perform a cost-effectiveness analysis to compare post-training endotherapy vs common practice vs laparoscopic surgery for management of LNPCPs.

3. STUDY DESIGN

A standard training program will be developed to improve endoscopic detection of LNPCPs, real-time diagnosis of the depth of SM invasion and endotherapy. We will examine the effect of additional training in a multicenter randomized controlled trial. Specifically, we will compare the safety (complication rate) and effectiveness (local recurrence at 6 months follow-up examination) of endoscopic resection in a group of at least 30 endoscopists who are exposed to a systematic training program on advanced endoscopic imaging, pit-pattern recognition and resection techniques vs 30 endoscopists doing regular training. The training package will comprise modern educational tools (e-learning modules, webinars, video-training). Hands-on training will be provided in animal models (ex-vivo).

The period of inclusion and follow-up will be from 2019-2021, where the duration of the individual patient will be 6 months.

A flow diagram of the study design is presented in the figure below.

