4.2 Randomisation, blinding and treatment allocation

Participating centers will be randomized to the *intervention group* vs. *control group*, as detailed in **Figure 1**. To mitigate the effect of contamination, i.e. exchange of knowledge, practical skills between participants, we prefer to randomize centers instead of endoscopists. In each center, two endoscopists will participate in the study. Both the control (n=30 endoscopists) and the intervention group (n=30 endoscopists) will receive an e-learning module regarding the OPTICAL I model focused on optical diagnosis of T1 carcinomas, and assessment of an EMR scar to recognize recurrence. In addition to this, the intervention group will receive an additional EMR training package, consisting of an e-module and a two-day symposium.

We will target our intervention (training) to this specific group because endoscopists at the beginning of their career may be more compliant to implement a change in their practice. An additional questionnaire will be used to provide baseline information regarding total number of endoscopic resections over the past year, resection techniques used (EMR vs ESD), the complication rate (bleeding, perforations) and the referral rate to surgery in order to select 20 endoscopists with comparable experience and endoscopic proficiency. We realize that such selection is associated with difficulty – baseline characteristics among the 2 groups will never be the same. Evaluation of such baseline information is, however, of importance for a meaningful interpretation of the study outcomes.

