4.3 Study procedures

4.3.1 Standard optical training and registration (control group)

A training package will be developed to train endoscopists in optical diagnosis based on the features in the OPTICAL I model (Paris classification, location, depression, easy friability and advanced imaging (NBI or chromoendoscopy)). The training will also concern the recognition of recurrence in a post-EMR scar. All participants will register a standardized and pre-defined set of parameters within their endoscopy report for every colonoscopy where a LNPCP >20mm is encountered or removed (Appendix A).

Because size, morphology, site and access to a lesion predict the completeness of resection (SMSA score) {Rutter, 2015}, the difficulty of endoscopic resection will be stratified according to the SMSA score (Figure 1). The features of the SMSA score will also be included in the standardized set of parameters.

Photo documentation will be performed by the endoscopists at the following moments:

1. During lesion assessment
 - a. In white light
 - b. Zoom with advanced imaging (e.g. NBI, I-scan)
2. After performing the EMR
 - a. Scar before adjunctive treatment
 - b. Scar after adjunctive treatment/before adjuvant treatment
 - c. Scar after adjuvant treatment

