- b. Zoom
- c. Zoom with advanced imaging modality (e.g. NBI, I-scan)

STEP 2: ENDOSCOPIC MUCOSAL RESECTION

1. EMR documentation in endoscopy report

- a. Lifting fluid → NaCl / Gelofusin/ Venofundin

- b. Dye included in the injection fluid →yes/no
- c. Adjuvant adrenalin in lifting fluid → yes/no?
- d. En-bloc or piecemeal?
- e. Number of pieces [n = ... / >10 fragments]
- f. Intraprocedural bleeding yes/no?
 - i. Number of intraprocedural bleedings
 - ii. Treatment intraprocedural bleeding
 - 1. Clipping
 - 2. Snare tip coagulation
 - 3. Coagulation grasper
 - 4. Adrenalin injection
- g. Residual tissue after EMR yes/no?
 - i. In case of residual tissue, adjunctive treatment?
 - 1. Cold avulsion with biopsy forceps
 - 2. Cold avulsion with thermal ablation (CAST)
 - 3. Hot avulsion
 - 4. Snare tip coagulation
 - 5. Suck and snare
 - 6. APC
- h. Adjuvant treatment performed to prevent recurrence yes/no?
 - i. Argon plasma coagulation
 - 1. Borders (y/n)
 - 2. Scar surface (y/n)
 - ii. Snare tip soft coagulation
 - 1. Borders (y/n)
 - 2. Scar surface (y/n)

2. Tattoo 2 cm distal at the same side (to make sure the scar can be retrieved during surveillance colonoscopy)

3. Photo/videodocumentation

- a. Recording first 5 EMRs (intervention group)
- b. Photodocumentation of the scar
 - i. Before adjunctive treatment
 - ii. Before adjuvant treatment
 - iii. After adjuvant treatment

STEP 3: AFTER COLONOSCOPY

- 1. Informing the patient about the study

2. Providing the information package
3. Note patient data on study list (patient number, sex, birthdate)
4. Schedule 6 month FU colonoscopy

STEP 4: SURVEILLANCE COLONOSCOPY AFTER 6 MONTHS

1. Endoscopy report

- a. Recurrence yes/no?
- b. Unifocal or multifocal [n]
- c. Size of largest recurrence (in mm)
- d. In case of recurrence, treatment yes/no?
 - i. Re-EMR
 - ii. Cold avulsion
 - iii. Cold avulsion with snare tip coagulation (CAST)
 - iv. Hot avulsion
 - v. Suck and snare
 - vi. eFTR
 - vii. ESD
 - viii. APC
 - ix. Snare tip soft coagulation (STSC)

2. Biopsy the scar

- a. Take a biopsy every 5 mm [e.g. in a scar of 18mm, 3 biopsies are taken]
- b. Present every biopsy in a separate PA jar

3. Photodocumentation

- a. Scar [white light, zoom and advanced imaging modality]

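### The control arm is labelled regular training, but both arms receive trial-developed optical and scar training, so the randomised contrast is only the added EMR package with expert feedback.

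*Protocol*

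**What the plan says.** Section 3 sets the trial up as a "systematic training program on advanced endoscopic imaging, pit-pattern recognition and resection techniques vs 30 endoscopists doing regular training". The Summary agrees: "The control group will comprise 30 endoscopists (from 15 centers) who receive regular training". For the economic question, the Summary speaks of "comparing post-training endoscopic resection vs. common endoscopy practice vs laparoscopic surgery", section 2.1.2 aims to "compare post-training endotherapy vs common practice vs laparoscopic surgery", and the Summary's endpoint list has "cost-effectiveness (post-training situation vs current situation vs laparoscopic surgery".

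The operational sections describe the arms differently. Under section 4.2 the control and intervention groups alike "will receive an e-learning module regarding the OPTICAL I model focused on optical diagnosis of T1 carcinomas, and assessment of an EMR scar", and the intervention group receives an EMR package on top. Section 4.3.1, whose heading names the control group, says: "A training package will be developed to train endoscopists in optical diagnosis based on the features in the OPTICAL I model". It lists advanced imaging among those features, adds training in recognising recurrence in a scar, and has all participants register the Appendix A items for every large lesion. Section 4.3.2 gives the intervention group alone the EMR training, hands-on and non-technical skills training, and expert feedback on recorded procedures.

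**The concern.** A reader of the Summary and section 3 would take the trial to test a whole programme (imaging, pit pattern and resection) against endoscopists left as they are. On the operational text, no arm is left as it is.

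This matters for three conclusions.

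- **A positive result** could be credited to the whole programme, although the optical-diagnosis module is given to both arms. The Summary's hypothesis names diagnosis before treatment as one of the routes to better outcomes, and section 2 treats judging invasion depth as a key step that bears on the choice of surgery. The shared part is therefore not incidental.
- **A null result** could be read as showing that training in general does not help, although both arms were trained.
- **The economic result** would be mislabelled if control-arm outcomes were reported as common practice or the current situation.

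**Working it through.** **1. The plan's own figure.** Section 3.1.4 asks for 683 lesions per group for 20% against 10% recurrence with 90% power and alpha 5% (taken as two-sided; the protocol does not say).

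- Two-proportion sample size: 266 per group.
- Design effect: 1 + (35 − 1) × 0.025 = 1.85, and 266 × 1.85 = 492.1.
- Efficiency loss of 10%: 492.1 / 0.9 = 546.8.
- Drop-out of 20%: 546.8 / 0.8 = 683.5.

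The figure reproduces, so the point does not rest on an arithmetic error. The 20% comes from meta-analysis data, and section 3.1.4 does not discuss it for a control arm that has had trial training.

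**2. What each arm receives.**

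| Component | Control | Intervention | Source |
|---|---|---|---|
| OPTICAL I optical diagnosis, including advanced imaging | yes | yes | 4.2, 4.3.1 |
| Recognition of recurrence in a scar | yes | yes | 4.2, 4.3.1 |
| Appendix A registration and photographs | yes | yes | 4.3.1, Appendix A |
| EMR e-module and two-day symposium | no | yes | 4.2 |
| Hands-on and non-technical skills training | no | yes | 4.3.2 |
| Expert feedback on first five recorded EMRs | no | yes | 4.3.2 |

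**3. The contrast that follows.** Write S for the first three rows, E for the EMR package (rows four and five) and F for the feedback. Control is S; intervention is S + E + F. Randomisation identifies the effect of E + F in the presence of S. No arm lacks S, so the effect of S, and of the whole programme over untrained practice, is not identified.

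**4. Set against the stated contrast.** Section 3 names three components.

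- Advanced imaging is among the features taught in the shared module.
- Pit-pattern recognition is not listed as taught in that module. Appendix A does ask every participant to record vascular and pit-pattern class, but recording is not teaching.
- Resection technique is taught only in the intervention arm.

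The stated contrast is therefore partly shared between arms, and regular training does not describe S.

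**5. The economic comparator.** It carries three labels: common endoscopy practice, common practice and current situation. Neither S nor S + E + F is any of these. The protocol does not say which data will represent that strategy. The section 4.2 baseline questionnaire covers past-year number of resections, techniques, complications and referral to surgery. It covers neither recurrence nor repeat colonoscopies, quality of life or costs, so it cannot supply the strategy alone. Using it would also replace a randomised comparison with a before-after one.

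**The case against.** The strongest reply is that the add-on design is disclosed. The Summary, section 3 and section 3.1.4 all speak of additional training, and section 4.2 says plainly what both arms get and what the intervention arm gets beyond it. The flow diagrams, which may show this too, are not visible in the text available. The shared elements also serve a purpose: common scar training, photographs, biopsies and registration help keep detection of recurrence equal between arms. All of this stands, and it is why the randomised comparison is internally valid. It does not reconcile section 3's explicit description of the control side with sections 4.2 and 4.3.1.

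A reader might infer more than the documents support:

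- **That the shared training dilutes the effect or the power by a known amount.** The protocol gives no recurrence rate for a control arm trained in this way. Even the direction is open, since scar training could raise detected recurrence.
- **That Appendix A amounts to resection training.** It is a reporting form. An item such as "Adjuvant treatment performed to prevent recurrence yes/no" may prompt practice, but nothing shows that it does.
- **That control-arm data will stand in for the current situation, or that the cost of the shared training will be left out.** The protocol states neither. Laparoscopic surgery has no randomised arm, so outside inputs are needed anyway.
- **That the imaging and diagnosis part of the programme is wholly untested.** Pit-pattern teaching is not listed in the shared module, so this cannot be said.

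**Conclusion.** The point holds as an inconsistency in how the comparator is described, with a real consequence for what may be concluded. The randomised contrast is shared optical training, scar training and registration, with versus without the EMR package and expert feedback. The trial can support a conclusion about that addition. It cannot support one about the shared optical-diagnosis training, nor about the whole programme against common practice.

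No numerical size is attached, because the documents give none. The comparison between arms is not biased by the shared elements, and the calculation of 683 per group stands on its stated inputs. The conclusion rests on reading sections 4.2 and 4.3.1 as the arms actually delivered.

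**What to change.** - **Sections 1, 2.1 and 3:** describe the control arm as in 4.2 and 4.3.1 (OPTICAL I optical diagnosis, scar recognition, Appendix A registration). State the tested contrast as the added EMR package plus individual expert feedback on the first five recorded EMRs, and limit the conclusion on benefit to it.
- **Shared scar training:** keep it, and say that it supports equal detection of recurrence in both arms.
- **Economic analysis:** label any trial-based comparison as EMR package plus feedback versus shared optical training and registration. Count the shared training cost in both arms. Do not call control-arm results the current situation.
- **Current-situation strategy, if kept:** name an external source for its inputs. For recurrence this could be the meta-analysis estimate of about 20% in 3.1.4, with the 15% and 13.1% quoted in section 2 as sensitivity values. Say that this comparison is not randomised.

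The cost is protocol wording, to be notified as an amendment under section 7.3, and a named source for the economic inputs. Randomisation, sample size and patient data collection do not change. The downside is a narrower claim.
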